4.2.2 Secondary objective

Comparison of database outcomes for non-extrafine beclomethasone dipropionate with Volumatic[®] spacer and non-extrafine beclomethasone dipropionate with Aerochamber[®] spacer in terms of Read codes for adverse reactions to beclomethasone dipropionate over a three-year period.

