5.4 Study design (database outcomes)

This is a historical database study composed of a 1-year baseline period for demographics, characterisation and matching. The index date is the date of prescription of a spacer (Volumatic[®] or Aerochamber[®]), with a 3-year outcome period for detection of adverse events. Patients will require 4 years' continuous practice data.

[figure not shown]

Figure 5: Study Design (database outcomes) extractions from 2005 onwards

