6.2 Inclusion and exclusion criteria (database outcomes)

Inclusion criteria

Diagnosis for asthma (confirmed by diagnostic Read code)

Age ≤65 years at index date for main outcomes, all ages for exploratory

4-years of continuous practice data comprising 1-year baseline data and 3-year outcome data

≥2 separate prescriptions of the beclomethasone pMDI in outcome year after index prescription date

Stepped down ICS in outcome period

Spacer prescription (Aerochamber or Volumatic)

Exclusion criteria

Received multiple types of ICS or FDC ICS/LABA during the baseline period, at the index date or during the outcome period

Prescribed both Aerochamber and Volumatic spacers

Table 7: Inclusion and exclusion criteria for database outcomes

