8.4.2 Secondary analysis – database outcomes

The total number of adverse events as listed in the Summary of Product characteristics in the outcome period will be compared between treatment groups compared using a conditional

Poisson regression model. The model will use empirical standard errors and adjustments will be made for potential baseline confounders.

The adjusted rate ratio with 95% confidence interval will be reported.

Exploratory analysis – The exacerbation rate and separately the daily SABA dosage for patients during the baseline year who step down ICS at the index date treated with an Aerochamber spacer will be compared to patients prescribed a Volumatic spacer and compared with a Wilcoxon ranked test.

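### Section 6.2 lets post-index prescribing decide who enters the database cohort, so adverse events can be deleted with the patient and the secondary rate ratio biased in either direction

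*Protocol*

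**What the plan says.** Section 5.4 of the protocol starts follow-up at the spacer: "The index date is the date of prescription of a spacer", "with a 3-year outcome period for detection of adverse events". The secondary objective (section 4.2.2) compares the two spacers "in terms of Read codes for adverse reactions to beclomethasone dipropionate over a three-year period", and section 8.4.2 analyses "The total number of adverse events as listed in the Summary of Product characteristics in the outcome period" with a conditional Poisson model.

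The table in section 6.2 (captioned Table 7) then defines the cohort partly by what happens in those three years:

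- a drug exclusion: "Received multiple types of ICS or FDC ICS/LABA during the baseline period, at the index date or during the outcome period";
- a spacer exclusion: "Prescribed both Aerochamber and Volumatic spacers", with no time window;
- a continued-use requirement: "≥2 separate prescriptions of the beclomethasone pMDI in outcome year after index prescription date";
- a dose requirement: "Stepped down ICS in outcome period".

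The same table asks for four continuous years of practice data, three of them after index.

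The questionnaire cohort in section 6.1 is built differently. Its drug exclusion ends at the index date, and its beclomethasone requirement lies in the year before index.

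**The concern.** Eligibility should be settled with what is known at index. Here it depends on prescribing that occurs while the outcome accrues, and that prescribing may be a response to the outcome. Take a patient who gets oral thrush (the first database outcome in section 7.4) in year one. If that patient is then moved to another ICS, to a fixed-dose combination or to the other spacer, or stops before a second prescription, both patient and event disappear. The step-down condition also selects on the later course of treatment; it might retain or remove patients with events, depending on what prompts the change.

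What is at stake is the secondary comparison. If the chance of being excluded after an event differs between spacers, the rate ratio no longer compares the groups as they stood at index. Matching (section 8.3) uses baseline data and the model (section 8.4.2) adjusts for baseline confounders; neither can repair selection that happens after index. Section 6.2 fixes the cohort itself, so a later model cannot recover patients who were never included.

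**Working it through.** **Is there a planned figure to reproduce?** None for this cohort. The only power calculation (section 8.1) belongs to the questionnaire analysis and does not bear on the point. The protocol also gives no rate of, or reason for, switching. Everything below is an illustration with assumed inputs.

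**Simple case.** Let p be the true 3-year risk of an event and s the share of patients with an event who are excluded afterwards. Assume that no event-free patient is excluded. Then

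observed risk = p(1 − s) / (1 − ps).

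Assume p = 0.15 on Aerochamber and 0.10 on Volumatic, a true ratio of 1.50 and a true difference of 5.0 points.

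| s, Aerochamber | s, Volumatic | Observed Aerochamber | Observed Volumatic | Ratio |
|---|---|---|---|---|
| 40% | 20% | 0.090/0.940 = 9.6% | 0.080/0.980 = 8.2% | 1.17 |
| 20% | 40% | 0.120/0.970 = 12.4% | 0.060/0.960 = 6.3% | 1.98 |
| 50% | 10% | 0.075/0.925 = 8.1% | 0.090/0.990 = 9.1% | 0.89 |
| 10% | 50% | 0.135/0.985 = 13.7% | 0.050/0.950 = 5.3% | 2.60 |
| 30% | 30% | 0.105/0.955 = 11.0% | 0.070/0.970 = 7.2% | 1.52 |

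Unequal exclusion moves the ratio either way, depending on which group loses more patients with events. Equal exclusion leaves the ratio near 1.50 but shrinks the difference from 5.0 to 3.8 points.

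**Letting event-free patients switch too.** With s1 the share excluded among patients with an event and s0 the share among those without,

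observed risk = p(1 − s1) / [p(1 − s1) + (1 − p)(1 − s0)].

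- Assume p = 30% in both groups, s0 = 10%, and s1 = 50% on Aerochamber and 30% on Volumatic. The observed risks are 0.15/(0.15 + 0.63) = 19.2% and 0.21/(0.21 + 0.63) = 25.0%. A true ratio of 1.00 appears as 0.77. With the two s1 values swapped it appears as 1.30.
- Assume p = 10%, s1 = 10% and s0 = 25%. The observed risk is 0.09/(0.09 + 0.675) = 11.8%, above the true 10%. If s1 = s0, the observed risk equals p.

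So absolute risks are understated only if patients with events are excluded more often than those without.

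These sums use the risk of at least one event. The planned analysis counts all events, so they show the mechanism and do not forecast the result.

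**The case against.** The strongest defence is attribution. The objective concerns reactions to beclomethasone over three years, and section 7.4 includes slow outcomes such as cataracts, glaucoma and osteoporosis. Time on another ICS or the other spacer would blur which exposure was responsible. That is a sound reason to stop counting at the switch. It is not a reason to delete events that came before it.

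It can also be objected that the protocol never says patients switch because of adverse events. This stands: such removal is an inference from the criteria, not a documented fact. Likewise, the spacer criterion does not say ever; it only lacks a window, so its literal reach includes the outcome period.

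A reader might infer that the bias favours the unlicensed pairing, because Table 2 shows Aerochamber Plus as unlicensed with Clenil Modulite and clinicians might change it sooner after a problem. The documents do not support that. Table 2 gives licence and fit, not switching behaviour. Section 3.0 describes the Volumatic as one of the larger spacers and notes that patients may be unwilling to carry or use such devices, which could mean more changes away from Volumatic. A reader might equally infer that event rates must be understated; as shown, that needs a further assumption.

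**Conclusion.** The point holds for the database analysis. Section 6.2 conditions entry on post-index prescribing during the period in which events are counted, and nothing in the protocol offsets it. The secondary rate ratio can be biased by an unknown amount in an unknown direction if event-related exclusion differs by spacer. Under the assumed risks and exclusion shares, a true ratio of 1.50 appears anywhere from 0.89 to 2.60; these figures rest wholly on the assumptions and are not estimates for this study.

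The outcome-period drug exclusion does not touch the primary non-inferiority conclusion, because the corresponding exclusion in section 6.1 stops at index. The change should be made, but it does not put the primary result at risk.

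**What to change.** In section 6.2:

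- apply the other-ICS, fixed-dose-combination and both-spacers exclusions to the baseline period and index date only;
- set the beclomethasone requirement at or before index, counting an index-date prescription so that patients who start the drug with the spacer are not lost;
- remove step-down in the outcome period as an entry condition for the adverse-event comparison, and keep it for the exploratory step-down question.

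In section 8.4.2:

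- assign patients to their index spacer and count events until the first of another ICS or fixed-dose combination, the other spacer, end of data, or three years, with log person-time as an offset in the planned Poisson model. The end-of-data rule has effect only if three complete outcome years are no longer required for entry;
- because censoring at switch may be informative, also report an analysis that follows switchers in their index group for all three years, and the number switching by group;
- keep the cohort without switchers as a sensitivity analysis.

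The cost is revised table wording, an offset term and one further analysis of data already held. The downside is small: switchers contribute shorter follow-up in the censored analysis and mixed exposure in the three-year one.

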6.3 Data source

The study will use patient data from the Optimum Patient Care Research Database (OPCRD).¹² The study team work with anonymous data removed of any patient identifiable

information. The OPCRDR is developed, maintained, and owned by Optimum Patient Care (OPC), a social enterprise company that aims to improve patient outcomes through medical research and services. OPC provides evidence-based recommendations to UK general practices through bespoke software and practice reports.

The OPCRDR currently comprises longitudinal medical records for over 2.5 million patients from over 550 primary care practices across the UK. The OPCRDR contains two types of data: (1) routinely recorded clinical data and (2) questionnaire responses from over 55,700 patients with respiratory conditions. The OPC questionnaires are a compilation of validated questions covering symptoms, disease control, triggers, side effects, quality of life, and unique adherence measures. OPCRDR is the only database in the UK that complements routinely recorded disease coding and prescribing information with patient-reported outcomes. The OPCRDR also links with nationwide practice prescribing data to enable targeted delivery of dataset needs.

A unique dataset is provided for each study with only the variables necessary to inform the study objectives included. Only studies that evaluate risk-benefit profiles of treatment options will report adverse events of treatments, ensuring confidentiality of data at all stages. The study will be performed in compliance with all applicable local and international laws and regulations, including without limitation ICH E6 guidelines for Good Clinical Practices. The database has received a favourable opinion from the Health Research Authority for clinical research use (REC reference: 15/EM/0150). Governance is provided by The Anonymous Data Ethics Protocols and Transparency (ADEPT) committee, an independent body of experts and regulators commissioned by the Respiratory Effectiveness Group (REG, <http://www.effectivenessevaluation.org/>) to govern the standard of research conducted on internationally recognised databases. All research using OPCRDR will be registered on established study databases such as the European Network of Centres for Pharmacoepidemiology and Pharmacovigilance (ENCePP, <http://www.encepp.eu/>).

7.0 Study variables and study outcomes

Refer to Appendices for detailed variable and outcome definitions, and mock tables of demographic and baseline variables and outcome results.

7.1 Demographic and baseline variables for patient questionnaire outcomes

- Gender (male/female)

- Age of patient (years, at index date)
- Body Mass Index (BMI, at time nearest index date, calculated from height and weight data if available, otherwise taken from practice-recorded BMI value, detailed definition in Appendix 1)
- Smoking status (identified by Read code, closest to index date)
- SABA daily dose calculated 1 year prior to index date*
- Percentage predicted peak flow (closest to index date)
- Total cumulative ICS dose
- Spacer type
- Total cumulative non-extrafine beclomethasone dipropionate therapy
- Duration of ICS therapy
- Number of exacerbations (ATS/ERS 2015 consensus definition[†]) from 1 year prior to index date
- Number of oral corticosteroid prescriptions from 1 year prior to index date
- Number of antibiotic prescriptions for lower respiratory tract infections from 1 year prior to index date
- History of comorbidities related to asthma:
 - Pneumonia (Read code diagnosis from 1 year prior to the index date)
 - Diabetes (Read code diagnosis and/or antidiabetic drugs ever prior to the index date)
 - Ischaemic heart disease (Read code diagnosis before one year prior to the index date)
 - Rhinitis (Read code diagnosis, including chronic and allergic rhinitis and prescriptions for nasal steroids between one year prior to index date)
 - Eczema (Read code diagnosis between one year prior to index date)
 - Osteoporosis (Read code diagnosis between one year prior to the index date)
 - Charlson Comorbidity Index (based on Read code diagnoses between one year prior to index date, detailed definition in Appendix 1)

7.2 Demographics and baseline variables for database outcomes

- Gender (male/female)

* Calculated as average number of puffs per day over the year multiplied by strength (in µg);
i.e. $\frac{\text{Number of inhalers} \times \text{doses per inhaler}}{365} * \text{strength}$

† See appendix 1 for definitions

- Age of patient (years, at index date)
- Body Mass Index (BMI, at time nearest index date, calculated from height and weight data if available, otherwise taken from practice-recorded BMI value, detailed definition in Appendix 1)
- Smoking status (identified by Read code, closest to index date)
- SABA daily dose calculated in baseline prior to index date*
- Percentage predicted peak flow (peak flow predicted, closest to index date)
- Total cumulative ICS dose
- Total cumulative non-extrafine beclomethasone dipropionate therapy
- Duration of ICS therapy
- Number of exacerbations (ATS/ERS 2015 consensus definition[†]) prior to index date
- Number of oral corticosteroid prescriptions prior to index date
- Number of antibiotic prescriptions for lower respiratory tract infections prior to index date
- History of comorbidities related to asthma:
 - Pneumonia (Read code diagnosis in the year prior to the index date)
 - Diabetes (Read code diagnosis and/or antidiabetic drugs ever prior to the index date)
 - Ischaemic heart disease (Read code diagnosis prior to the index date)
 - Rhinitis (Read code diagnosis, including chronic and allergic rhinitis and prescriptions for nasal steroids prior to index date)
 - Eczema (Read code diagnosis prior to index date)
 - Osteoporosis (Read code diagnosis prior to the index date)
 - Charlson Comorbidity Index (based on Read code diagnoses in the year prior to index date, detailed definition in Appendix 1)

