5.3 Sub analysis

1. Characterisation of patients in terms of demographics, baseline variables and patient-reported outcomes (BLF Questionnaire) by age group (<16, 16–65, all ages, >65 as an exploratory group)
2. Characterisation of patients in terms of demographics, baseline variables and adverse events by prescription for high daily ICS dose (>500 µg fluticasone equivalence/1000 µg beclomethasone dipropionate) defined as ≥1 prescription for 1000 µg beclomethasone dipropionate during the baseline period
3. Characterisation of patients in terms of demographics, baseline variables and patient-reported outcomes (BLF Questionnaire) by high daily ICS dose (>500

μg fluticasone equivalence/1000 μg beclomethasone dipropionate) calculated as an average daily ICS dose* during the baseline period

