7.5 Step down outcomes

- 1) Number of severe exacerbations in baseline year
- 2) Daily average SABA category in baseline year

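### SABA daily dose multiplies puffs by raw microgram strength with no conversion between reliever drugs, so pooling different SABAs would mis-score use in the categories and the exploratory step-down comparison

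*Protocol*

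**What the plan says.** Section 7.1 lists "SABA daily dose calculated 1 year prior to index date" as a baseline variable for the questionnaire cohort. Section 7.2 lists "SABA daily dose calculated in baseline prior to index date" for the database cohort. Both entries carry the same footnote: "Calculated as average number of puffs per day over the year multiplied by strength", in micrograms. The formula given with it is number of inhalers times doses per inhaler, divided by 365, times strength. It has no equivalence factor and no summation over products.

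The variable is used in these places:

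- Section 7.5 names as a step-down outcome "Daily average SABA category in baseline year".
- The exploratory paragraph of 8.4.2 instead compares "separately the daily SABA dosage for patients during the baseline year who step down ICS at the index date" between spacers with a Wilcoxon test.
- The mock baseline tables in Appendix 2 show SABA dose both as a continuous variable and as Low/Medium/High.
- Section 8.3 does not name SABA. It says that indicators of disease severity will be considered for matching, and 8.4 allows adjustment for baseline confounders.

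The criteria in 6.1 and 6.2 exclude patients who received multiple ICS types but are silent on SABA type. Appendix 1 defines BMI, exacerbation and the Charlson index, not SABA use.

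**The concern.** Micrograms of two different drugs need not represent the same amount of reliever effect. The protocol acknowledges this for inhaled steroids when it sets its high-dose threshold as "fluticasone equivalence/1000" µg beclomethasone dipropionate, with 500 µg fluticasone on the other side. For SABA it fixes a rule that treats all micrograms alike.

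Two patients with the same reliever need but different SABA drugs would then receive different scores, for a reason unrelated to asthma control. SABA use is one of only two step-down outcomes, so such mis-scoring would bear directly on the exploratory question of whether one spacer gives better control before step-down. As a baseline severity marker it could also reach matching or adjustment if it is selected there.

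**Working it through.** The protocol reports no SABA figure, so there is nothing to reproduce. It also names no SABA product, strength or mix. Every strength, share and usage distribution below is therefore an assumption, shown as a range.

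**1. The formula at equal use.** Assume 12 inhalers of 200 doses in the year: 12 × 200 / 365 = 6.58 puffs/day. The protocol score is then:

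| Assumed strength (µg/puff) | Score (µg/day) |
|---|---|
| 100 | 658 |
| 200 | 1315 |
| 250 | 1644 |
| 500 | 3288 |

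The score scales one-for-one with strength: a factor of 1 if one strength is in use, 5 at an assumed 5:1 ratio. This is mis-scoring only to the extent that the products differ in potency per microgram. The steps below take the extreme case in which one puff of each product does the same work.

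**2. Ratio of arm means at equal puffs.** Let k be the strength ratio and q the share of patients on the stronger-labelled product in each arm. The ratio is (1 − q₂ + k·q₂) / (1 − q₁ + k·q₁).

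- Equal mix, 5% and 5%: 1.00 for any k.
- 5% versus 10%: 1.10/1.05 = 1.05 (k = 2); 1.40/1.20 = 1.17 (k = 5).
- 2% versus 10%: 1.10/1.02 = 1.08 (k = 2); 1.40/1.08 = 1.30 (k = 5).

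**3. Wilcoxon rejection at a nominal 5% when true use is equal.** These are simulations with 2,000 to 4,000 replicates per scenario. Arms of 100 and 300 use log-normal puffs/day (median 2, log-SD 0.8). The 147/293 row borrows the arm sizes from 8.1 and uses a Poisson mean of 5 inhalers of 200 doses.

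| Arm sizes | Shares | k = 2 | k = 5 |
|---|---|---|---|
| 100/100 | 2% vs 10% | about 7% | about 13% |
| 300/300 | 2% vs 10% | about 12% | about 30% |
| 147/293 | 2% vs 10% | about 15% | about 23% |
| 147/293 | 5% vs 5% | 5.6% | 5.3% |

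With one strength (k = 1) the 147/293 model rejects 5.0% to 5.9%. The excess therefore comes from unequal mix, not from the formula alone.

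**4. Power when the mix is equal.** For a true 1.4-fold difference at 100 per arm and k = 5, power is about 82% when use is scored on a common scale. On raw micrograms it falls to about 77% (5% in both arms) or 72% (10% in both arms).

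**5. Category misplacement.** The protocol gives no cut-offs, so assume a High category at 600 µg/day, which is six puffs of a 100 µg product. Under the log-normal model, P(puffs ≥ 6) = 0.085, P(puffs ≥ 3) = 0.306 and P(puffs ≥ 1.2) = 0.738.

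- q = 2%, k = 2: 0.02 × (0.306 − 0.085) / (0.98 × 0.085 + 0.02 × 0.306) = 0.0044/0.0893 = 5%.
- q = 10%, k = 5: 0.10 × (0.738 − 0.085) / (0.90 × 0.085 + 0.10 × 0.738) = 0.0653/0.150, about 43%.

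Between 5% and about 43% of those labelled High would be there because of product strength.

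**The case against.** The strongest reply is that the size of the effect comes entirely from the inputs chosen. The protocol gives no SABA strengths and no product mix, and nothing in it links reliever product to spacer type. With a single drug the formula is harmless, and with an equal mix the rank test holds its level. This stands: a reader might infer a several-fold scoring error or a biased spacer comparison in these data, and the document supports neither without assumptions. What remains is that the written rule gives no protection if the condition occurs.

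Second, puffs times strength is a legitimate daily dose. When one drug comes in several strengths it is the right quantity, and plain puffs/day would lose real dose information. This also stands, and it is why simply deleting the strength factor is not the main remedy.

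Third, the contrast with ICS is weaker than it looks. The fluticasone equivalence appears only in the high-dose threshold; the protocol's own average daily ICS dose formula also multiplies by raw strength with no conversion. This is correct, though for ICS the exclusion of patients on multiple types partly covers the gap, and SABA has no such restriction.

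Fourth, product equivalence is often left to an analysis plan. Here, however, the protocol states the formula explicitly for both cohorts, so the point concerns a rule that has been fixed, not a missing detail.

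**Conclusion.** The point holds conditionally and is minor. As written, the formula mis-scores reliever use whenever SABA drugs with non-equipotent micrograms are pooled, and nothing in the protocol prevents that pooling. The consequence is misplacement in the SABA categories and lost power in one exploratory outcome. Between-spacer bias follows only if the product mix differs by spacer: rejection of about 7% to 30% at a nominal 5%, under assumed shares of 2% versus 10% and strength ratios of 2 to 5.

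Two stronger readings are not supported. The protocol does not say that patients will be matched on SABA: 8.3 makes severity indicators candidates for selection and makes matching of step-down patients depend on numbers, so an effect there is possible, not established. Nor is the primary conclusion put in doubt: the non-inferiority criterion in 8.4.1 concerns oral thrush or hoarseness and is not an analysis of SABA.

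**What to change.** In the footnote to 7.1 and 7.2, convert each SABA product to one stated reference-SABA equivalent before multiplying, and sum over all SABA products prescribed in the year. Name the reference product and list the conversion factors with their source. Build the Low/Medium/High categories on that scale, and use it for the step-down outcome and wherever SABA is selected for matching or adjustment.

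In the same edit, reconcile 7.5, which makes the step-down outcome a category, with 8.4.2, which tests the daily dosage. State which is analysed and fit the test to it.

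Puffs per day can be reported as a sensitivity measure; its small drawback is that it ignores real dose differences when one drug comes in several strengths.

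The cost is a few lines of text and a short conversion table. No new data are needed beyond the prescription records the formula already uses. If only one SABA drug turns out to be in use, ranks are unchanged.
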